# Study drug dispensation

- Patients may be supplied with additional study drug during a visit if there is a concern that the
  patient may not be able to report to the site as scheduled for the next required visit. This will
  ensure that patients have enough study drug to accommodate extended visit windows or
  telehealth visits.
- In some circumstances, it may be necessary to ship study drug directly to the patient. Shipping will be performed by a qualified professional courier who is contracted by the Sponsor or Contract Research Organization. The courier will be responsible for providing packing materials and cold chain monitoring to complete the shipment. Patients must consent to providing personal data to the courier to complete the shipment. Refer to the Pharmacy Manual for additional details.

COVID-19	Coronavirus Disease 2019
CRF	Case report form
CSR	Clinical Study Report
cT1	Iron-corrected T1
DSMC	Data Safety Monitoring Committee
ECG	Electrocardiogram
eCRF	Electronic case report form
ELF	Enhanced liver fibrosis
ET	Early Termination
GGT	Gamma glutamyl transferase
HOMA-IR	Homeostatic Model Assessment for Insulin Resistance
hsCRP	High-sensitivity C-reactive protein
ITT	Intent-to-Treat
LS	Least square
MedDRA	Medical Dictionary for Regulatory Activities
mITT	Modified Intent-to-Treat
MMRM	Mixed-Model Repeated Measures
MNAR	Missing not a random
MRI	Magnetic resonance imaging
MRI-PDFF	Magnetic resonance imaging-proton density-fat fraction
NAS	Nonalcoholic Fatty Liver Disease Activity Score
NASH	Nonalcoholic steatohepatitis
PK	Pharmacokinetic(s)
PP	Per-Protocol
Pro-C3	N-terminal type 3 collagen propeptide

Abbreviation	Definition
SAE	Serious adverse event
SAP	Statistical Analysis Plan
STDM	Standard Data Tabulation Model
TEAE	Treatment-emergent adverse event
TEAESI	Treatment-emergent adverse event of special interest
TESAE	Treatment-emergent serious adverse event
TFL	Tables, Figures and Listings
T _{max}	Time to reach the maximum observed plasma concentration
WHO	World Health Organization
V _z /F	Apparent volume of distribution

1 INTRODUCTION

The purpose of this Statistical Analysis Plan (SAP) is to provide a description of the statistical methods to be implemented for the analysis of data from the study with protocol number NST-02. The SAP will be finalized prior to database lock. Any deviations from the SAP after database lock will be documented in the final Clinical Study Report (CSR).

2 STUDY OVERVIEW

2.1 Study Objectives

2.1.1 Primary Objective

The primary objective is to evaluate the efficacy of different doses of NST-4016 on the resolution of nonalcoholic steatohepatitis (NASH) without worsening of fibrosis in patients with NASH without histological or clinical evidence of cirrhosis.

2.1.2 Secondary Objective

The secondary objectives of the study are:

- To determine the safety and tolerability of NST-4016 in patients with NASH
- To characterize the pharmacokinetics (PK) of NST-4016

2.2 Study Design

2.2.1 Overview

This was a 52-week (62 week, including screening and follow-up), multicenter, randomized, double-blind, placebo-controlled, parallel-group study in male and female patients with a histological diagnosis of NASH. Approximately 264 patients were to be randomized into 1 of 3 parallel treatment groups (300 mg NST-4016, 600 mg NST-4016 or Placebo); randomization was stratified by baseline biopsy fibrosis score (2 levels: F1 or F2 /F3).

[figure not shown]
The study included a screening period, double-blind treatment period, and post-treatment followup. The Screening Visit could occur up to 8 weeks prior to randomization at Visit 2 (Week 0). The double-blind treatment period entailed 52 weeks of dosing with study drug and was to be followed by a Safety Follow-up Visit 2 weeks after the last dose of study drug. The study design is depicted in Figure 1 – Study Design.

Study drug dosing was to begin at Visit 2 (Week 0) and continue daily for 52 weeks. All patients were instructed to take 2 capsules of study drug (either 300 mg NST-4016 and/or matching placebo) orally in the morning with water once daily for 52 weeks. In the event that the Visit 9 biopsy was delayed, patients continued to administer study drug daily until the biopsy occurred, for up to 30 days after the originally projected Visit 9 date.

During the 52-week treatment period, patients were to return to the clinic for study visits every 1 to 3 months.

An external, independent Data Safety Monitoring Committee (DSMC) reviewed all available unblinded preliminary safety and biomarker results per the DSMC Charter.

Figure 1 – Study Design

In addition, the following data was reviewed during an interim analysis, which was performed after 90 patients completed 16 weeks of treatment: alanine aminotransferase (ALT), aspartate aminotransferase (AST) and AST/ALT ratio, Homeostatic Model Assessment for Insulin (HOMA-IR), Pro-C3, Enhanced Liver Fibrosis (ELF) panel, magnetic resonance imaging-proton density-fat fraction (MRI-PDFF), Iron-corrected T1 (cT1) and lipid parameters. The DSMC reviewed summary statistics and made recommendations which were shared blindly with the sponsor and clinical sites.

2.2.2 Sample Size Determination

A sample size of 88 patients per treatment group provides 80% power to detect a treatment effect of 22% (40% responder rate for active versus 18% placebo), assuming a dropout rate of 25%.

2.3 Study Endpoints/Parameters

2.3.1 Primary Efficacy Endpoint

The primary efficacy endpoint is the percentage of patients with resolution of NASH, defined as disappearance of ballooning (score = 0) with lobular inflammation score 0 or 1, and with no worsening of fibrosis.

2.3.2 Key Secondary Efficacy Endpoints

The key secondary efficacy endpoints are:

Percentage of patients with

- fibrosis improvement, defined as greater than or equal to one stage of fibrosis improvement and no worsening of steatohepatitis (inflammation/ballooning)
- resolution of NASH (defined as disappearance of ballooning (score = 0) with lobular inflammation score 0 or 1 AND fibrosis improvement (defined as greater than or equal to one stage of fibrosis improvement)

2.3.3 Other Secondary Efficacy Endpoints

Percentage of patients with:

- fibrosis improvement, defined as greater than or equal to one stage of fibrosis improvement
- 2-stage fibrosis improvement, defined as greater than or equal to two stages of fibrosis improvement

Change from baseline in:

- Liver enzymes AST, ALT, alkaline phosphatase (ALP), gamma glutamyl transferase (GGT), and bilirubin
- Inflammation marker high-sensitivity C-reactive protein (hsCRP)
- Fibrosis activity markers N-terminal type 3 collagen propeptide (Pro-C3) and ELF panel
- HOMA-IR, a measure of insulin resistance and metabolic status.
- Composite Disease Activity Score composite NASH score of inflammation, ballooning, fibrosis
- Nonalcoholic Fatty Liver Disease Activity Score (NAS)
- Individual histological scores for steatosis, ballooning, inflammation, and fibrosis
- Imaging parameters MRI-PDFF

2.3.4 Exploratory Parameters

Exploratory biomarkers and endpoints of serum and tissue lipidomics and AI Histology from Path AI and/or Histolndex and cT1 will be reported in a supplemental CSR if and when available.

2.3.5 Pharmacokinetic Parameters

The following PK parameters will be summarized:

• NST-4016 concentrations (all patients)

In addition, for the Intensive PK subset:

- AUC_{0-t}
- AUC_{0-inf}
- CL/F
- C_{max}
- T_{max}
- V_z/F

2.3.6 Safety Parameters

The safety endpoints include:

- Adverse events (AEs)
- Serious AEs (SAEs)
- Adverse events of special interest (AESI) suspected drug induced liver injury.
- Vital signs
- Physical examinations
- Electrocardiograms (ECGs)
- Clinical laboratory parameters

3 STATISTICAL METHODOLOGY

3.1 General Considerations

3.1.1 Analysis Day

Analysis day will be calculated from the date of first dose of study drug. The day of the first dose of study drug will be Day 1, and the day immediately before Day 1 will be Day -1. There will be no Day 0.

3.1.2 Analysis Visits

Scheduled visits will be assigned to analysis visits as recorded on the electronic case report form (eCRF). Unscheduled and early termination visits will be assigned to analysis visits according to the visit windows described in the following table:

Analysis Visit	Target Analysis Day	Low Analysis Day	High Analysis Day
Visit 2 (Week 0)	1	NA	NA
Visit 3 (Week 4)	28	2	49
Visit 4 (Week 10)	70	50	91
Visit 5 (Week 16)	112	92	140
Visit 6 (Week 24)	168	141	196
Visit 7 (Week 32)	224	197	252
Visit 8 (Week 40)	280	253	322
Visit 9 (Week 52)	364	323	371
Visit 10 (Week 54) Safety FUP	378	372	

If there is more than one assessment within a visit window, then the analysis visit will be assigned by the following priorities:

- 1. Use the assessment from the visit with the matching visit label.
- 2. Use the visit closest to the target visit day; in the case of ties, use the earlier visit.

Further details of analysis visit assignment will be provided in the Analysis Data Model (ADaM) Specifications

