# 6.5 Early Termination Visit and Withdrawal Procedures

The end of treatment for patients completing the study is Visit 9 (Week 52). For patients who are withdrawn from the study prior to completion, all Visit 9 procedures will be performed at an ET Visit. Liver biopsy at ET will only be performed for patients who have been on study drug for at least 6 months.

Patients who discontinue early from the study for any reason prior to completion of the treatment period will be requested to return to the clinic for an ET Visit as soon as possible after their last intake of study drug.

If a patient discontinues early from the study for any reason after completion of the treatment period but before the Safety Follow-up Visit, sites should make every attempt to bring the patient into the site for the Safety Follow-up Visit.

The following procedures will be performed at the ET Visit:

- Record concomitant medications.
- Measure body weight.
- Perform complete physical examination.
- Collect vital signs (blood pressure [3 readings], pulse rate, and body temperature) with the patient in the sitting position after 5 minutes of rest and before any blood draws.
- Collect fasting blood sample for the following:
  - o Hematology, biochemistry, coagulation, and lipid panels.
  - Lipoprotein particle size.
  - o Biomarkers (HOMA-IR, hsCRP, Pro-C3, and ELF panel).
  - o Serum pregnancy test (only for women of childbearing potential).
  - o Lipidomic analyses (in a subgroup of patients).
- Collect urine sample for urinalysis.
- Perform 12-lead ECG after the patient has been resting in the supine position for at least 10 minutes.
- Perform MRI-PDFF and cT1 imaging.
- Perform liver biopsy (if patient has been on study drug for at least 6 months) for analyses (including lipidomics in a subset of patients).
- Assess adverse events.
- Collect a PK blood sample.
- Collect returned and used/unused study drug and assess compliance.

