3.1.5 Hypothesis Testing

Given the primary and key secondary endpoints along with 2 active doses, hypothesis testing will be performed in a hierarchical order to preserve the overall Type 1 error.

The 600mg dose will be tested first vs placebo. The primary and the 2 key secondary endpoints will be tested in the order as presented in section 2.3.2. Testing of these 3 endpoints will next move to the 300mg dose arm vs placebo. If during the sequential testing of these 6 hypotheses, a p-value is non-significant (at alpha = 0.05), the remaining (from that point onwards) p-values will be considered nominal and significance cannot be claimed.

No multiplicity adjustments will be applied for other secondary endpoints and exploratory parameters analysis. Since the testing of the other secondary endpoints will not involve any control of Type 1 error, all associated p-values are deemed to be nominal.

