3.2.3 Modified Intent-to-Treat (mITT) Population

The mITT Population will include all patients from the ITT Population who have valid baseline and Week 52 (or ET, if applicable) liver biopsy measurements; a valid Week 52/ET liver biopsy is

NorthSea Therapeutics B.V.	CONFIDENTIAL	Statistical Analysis Plan
Protocol NST-02		Version 1.0, 14 February 2023

defined as a liver biopsy that has occurred within 90 days of last dose/Week 52 visit. This will be the primary population for efficacy analysis.

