3.4 Efficacy Assessment

All efficacy analyses will be performed using the mITT Population and repeated in for the ITT Population. Analyses of the primary and all secondary endpoints will also be repeated for PP Population. All efficacy data will be listed.

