3.4.2.2 Nonalcoholic fatty liver disease activity score (NAS)

The NAS measures disease changes by scoring features of NASH during therapeutic trials. The total NAS represents the sum of scores for steatosis, lobular inflammation, and ballooning, and ranges from 0 to 8.

The change from baseline to Week 52/ET in NAS and individual histological scores (steatosis, ballooning, inflammation, and fibrosis) and a composite Disease Activity Score of inflammation, ballooning and fibrosis will be analyzed using an analysis of covariance model (ANCOVA). The model will be adjusted for treatment (300 mg NST-4016, 600 mg NST-4016, or placebo), biopsy

fibrosis score (2 levels: F1 or F2/F3), and respective baseline score. Pairwise treatment comparisons between each NST-4016 dose and placebo will be estimated using least square (LS) means, standard errors, 95% confidence intervals, and p-values. Sample SAS code is below.

A sensitivity analysis will also be conducted for the NAS and individual histological scores withi an ANCOVA model replacing the stratification factor of baseline biopsy score with the baseline ballooning score (1 or 2).

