3.4.2.3 Liver Enzymes

Liver enzymes are assessed at Screening, Visit 2 (Week 0), Visit 3 (Week 4), Visit 4 (Week 10), Visit 5 (Week 16), Visit 6 (Week 24), Visit 7 (Week 32), Visit 8 (Week 40), Visit 9 (Week 52), Visit 10 (Week 54) and at the ET Visit.

The change and percent change from baseline in AST, ALT, ALP, GGT and total bilirubin at each scheduled visit will be analyzed using a Mixed Model Repeated Measures (MMRM) model, with change (or percent change) from baseline as the dependent variable, adjusting for treatment (300 mg NST-4016, 600 mg NST-4016, or placebo), visit, treatment-by-visit interaction, biopsy fibrosis score (2 levels: F1 or F2/F3); and baseline score. The Restricted Maximum Likelihood (REML) estimation approach will be used with an unstructured covariance matrix. The LS means, standard errors, 95% confidence intervals, and p-values for the pairwise treatment comparisons between each NST-4016 dose and placebo will be estimated for each visit.

At visits where the fasted status of the patient is recorded (Visit 2 (Week 0), Visit 5 (Week 16) and Visit 9 (Week 52)), only samples taken in a fasted state will be included. All results from other visits will be included. An additional analysis will be carried out to include patients who we fasted at all three visits where fasted status is recorded.

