3.4.2.7 MRI-PDFF

Hepatic imaging by MRI will be performed at Screening, Visit 5 (Week 16) and Visit 9 (Week 52)/ET. Images will be assessed centrally for MRI-PDFF.

The change from the baseline to Week 16 and Week 52/ET in MRI-PDFF will be performed using similar ANCOVA models as described above. The change from baseline to Week 16 and Week 52/ET will be analyzed in separate models.

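### Do the day windows in SAP 3.1.2 clash with the pooled Week 52/ET time point used for histology and MRI-PDFF?

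*SAP*

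**What the plan says.** SAP 3.1.2 keeps scheduled visits as labelled on the eCRF. For the rest, "Unscheduled and early termination visits will be assigned to analysis visits according to the visit windows described in the following table". The Week 16 window is Days 92 to 140 and the Week 52 window is Days 323 to 371. Within a window, a record carrying the matching visit label takes priority. The section ends by leaving further detail to the ADaM specifications.

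The endpoint sections are worded differently. SAP 3.4.2.2 analyses "The change from baseline to Week 52/ET in NAS and individual histological scores" by ANCOVA. SAP 3.4.2.7 says of MRI-PDFF: "The change from baseline to Week 16 and Week 52/ET will be analyzed in separate models". The mITT Population takes ITT patients "who have valid baseline and Week 52 (or ET, if applicable) liver biopsy measurements", and SAP 3.4 adds: "All efficacy analyses will be performed using the mITT Population and repeated in for the ITT Population".

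Protocol 6.5 limits the ET biopsy: "Liver biopsy at ET will only be performed for patients who have been on study drug for at least 6 months". It sets no such minimum for the ET scan. Change in liver enzymes "at each scheduled visit will be analyzed using a Mixed Model Repeated Measures (MMRM) model" with an unstructured covariance matrix (SAP 3.4.2.3), and SAP 3.4.2.4 to 3.4.2.6 reuse a similar model for hsCRP, Pro-C3, ELF and HOMA-IR. For all other secondary endpoints, "all associated p-values are deemed to be nominal" (SAP 3.1.5).

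**The concern.** One SAP section sorts ET records by study day and another pools them with Week 52, with no statement of precedence. Three things could turn on this.

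- **Histology.** Literal windowing sends ET biopsies taken before Day 323 to Visits 6 to 8, where no histology analysis exists. The NAS and component-score ANCOVAs would then lose patients whom the mITT definition admits.
- **MRI-PDFF.** Pooling treats an early scan as a Week 52 value; windowing removes it from the Week 52 model.
- **Blood markers.** Windowing could create extra visits populated only by dropouts. Some pairs of those visits would share no patients, so an unstructured covariance could not be fully estimated, and the SAP names no fallback structure.

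At stake is which patients contribute to several Week 52 estimates, a choice best fixed before unblinding.

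**Working it through.** **1. The plan's own figure.** Inputs (SAP 2.2.2; Protocol 9.2.1.1): 40% versus 18%, two-sided alpha 0.05, 80% power, 25% dropout. With pooled variance and no continuity correction:

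n = [1.960 × √(2 × 0.29 × 0.71) + 0.842 × √(0.40 × 0.60 + 0.18 × 0.82)]² / 0.22² = 65.6, so 66 per arm.

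66 / (1 − 0.25) = 88, which matches the plan. Expected dropouts are 88 × 0.25 = 22 per arm. The ET rule plays no part in this figure.

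**2. Where the windows send ET records.** These are counts of possible days, not patients.

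- Biopsy, taking 6 months as Day 183 (assumption): Days 183 to 363 are 181 days. Visits 6, 7 and 8 take 14 + 56 + 70 = 140, and Week 52 takes 41 (23%).
- MRI: Days 2 to 363 are 362 days. Week 52 takes 41, Week 16 takes 49, and 272 fall at visits with no planned MRI-PDFF analysis.

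The textual conflict is therefore real.

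**3. Histology: what the other sections imply.** SAP 3.1.6 and 3.4.1 make a patient a non-responder only if neither a Week 52 nor an applicable ET biopsy is available. SAP 3.2.3 judges validity by a 90-day distance from last dose or the Week 52 visit, not by study day. Protocol 6.5 makes the ET Visit a performance of the Visit 9 procedures. SAP 3.4.2.2 names the pooled time point outright. All of these agree, and windowing would lead to visits with nothing to analyse.

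Size if an analyst did take the literal reading, assuming even dropout (22/363 per day per arm), 66 completers and every ET Visit attended:

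- ET biopsies, Days 183 to 364: 182 × 22/363 = 11.0, so N = 77.0 per arm.
- Of these, before Day 323: 140 × 22/363 = 8.5, so N = 68.5 if they are removed.
- Standard error ratio: √(77.0/68.5) = 1.06.

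At 25% attendance: 2.8 and 2.1 biopsies, N = 68.8 and 66.6, ratio √(68.8/66.6) = 1.02. At zero attendance nothing changes.

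**4. MRI-PDFF.** Under pooling, on the same assumptions, the share of Week 52/ET values that predate Day 323 is:

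- mITT: 8.5/77.0 = 11% at full attendance; 2.1/68.8 = 3% at 25%.
- ITT repeat (Days 2 to 322, 321 days): 321 × 22/363 = 19.5, and 19.5/88 = 22%; at 25% attendance, 4.9/71.5 = 7%.

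Turning these shares into bias needs a time course for the effect. The documents give none that supports a growing effect: Protocol 1.4.1.2 reports from the 16-week interim that liver fat did not change on either dose. A percentage shrinkage of a difference reported as absent would mean little.

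**5. Blood markers.** SAP 3.4.2.4 to 3.4.2.6 list Visit 2, Visit 5 and Visit 9/ET. The model covers scheduled visits, so each marker has two post-baseline visits and the unstructured matrix has 2 variances + 1 covariance = 3 parameters, informed by the patients seen at both. Extra visits arise only if an analyst adds weeks at which the marker was never scheduled. These sections also require a fasted sample, and SAP 3.4.2.3 lists fasted status as recorded at Visits 2, 5 and 9, so it is uncertain whether ET samples enter at all.

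**The case for a change.** The best case for a change is that a specific section overriding a general one is only a convention; the SAP does not state it, and 3.1.2 is written without exception. MRI-PDFF has no supporting text of the kind that settles biopsies, and ET scans can come from any point in treatment. Protocol 9.2.1.4 names Week 16 and Week 52 for imaging with no mention of ET. Using an early scan at Week 52 also resembles carrying a value forward, which sits awkwardly with the no-imputation rule in SAP 3.1.6. Membership of a Week 52 estimate arguably belongs in the SAP rather than in a programming document.

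What stands is narrow: the SAP does not say which rule governs an ET scan taken before Day 323, and the ADaM specifications that may settle it cannot be seen here. The obvious remedies add little. For biopsies and markers they would write down what the text already implies. For MRI-PDFF, letting the windows govern would discard a scan while the same patient's same-day biopsy counted as end of treatment; pooling keeps both but mixes exposure times. Reasonable statisticians would differ, and the sponsor has written the pooled form.

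**Conclusion.** The wording conflict exists, but it is a gap that analysts will fill sensibly, and no change to the plan follows. The day windows suit the laboratory series collected at every visit. Biopsies have a consistent end-of-treatment rule elsewhere in the SAP, and the marker models are bounded by their own schedules. The remaining question, early ET scans for MRI-PDFF, is a fair trade-off on an endpoint with nominal p-values.

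The size is small. Even the literal reading of the histology rule would widen standard errors by only about 2% to 6% at 25% to 100% ET attendance, and by nothing if no ET Visits take place. This rests on assumed even dropout of 22 per arm and 6 months taken as Day 183. It is generous to the concern, because the sample size inflation treats those 22 as lost, whereas here up to 11 of them supply biopsies. The primary and key secondary responder analyses follow their own ET biopsy rule (SAP 3.4.1 and 3.4.2.1) and are unaffected.

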3.1.3 Definition of Baseline

Baseline is defined as the value at the Screening Visit for the liver biopsy and imaging data and as the predose value at Visit 2 (Week 0) for the biomarker data. For all other efficacy and safety endpoints, baseline is defined as the predose value at Visit 2 (Week 0); if this value is missing, then the latest predose value is used.

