- 6. Has a PDFF ≥8% on MRI at screening, per the central imaging reader. The MRI-PDFF criteria will not apply if the patient has a qualifying historical liver biopsy.

- 7. Has ALT and AST <5 × upper limit of normal (ULN) and AST ≥20 U/L in men and ≥17 U/L for women upon entry into the study. A documented AST ≥30 U/L by a local laboratory within 60 days of screening will also be acceptable. The minimum AST criteria will not apply if the patient has a qualifying historical liver biopsy.
- 8. Has stable baseline liver enzymes, including serum ALT, AST, ALP, and total bilirubin values that are established by at least 2 samples demonstrating the following:
  - a. Values of an enzyme in the 2 samples are within  $1.5 \times ULN$  ranges.

OR

b. If one of the enzyme levels is >1.5 × ULN, the variability between the 2 samples of ALT and AST does not exceed 50% and the variability between the 2 samples of ALP and total bilirubin does not exceed 30%.

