# 8.7 Clinical Laboratory Evaluations

Clinical safety laboratory parameters will be measured or calculated at all study visits (see Appendix A). Fasting hematology, biochemistry, coagulation, and lipid panels and urinalysis parameters will be evaluated at all study visits. Further analysis of urine sediment or urine microscopy will be performed if there are any abnormalities on any of the following 3 dipstick results: leukocyte esterase, blood, or nitrite. Although lipid parameters will be evaluated at every visit, lipoprotein particle size will be assessed only at baseline, Week 16, and at the end of treatment (Week 52/ET). Lipid parameters will be monitored throughout the follow-up period and any lipid-lowering treatment started during the study should be reviewed during the follow-up period and adjusted or discontinued in accordance with the 2018 AHA/ACC Guideline on the Management of Blood Cholesterol. See Appendix F for links to the full and abbreviated versions

of the 2018 AHA/ACC Guideline on the Management of Blood Cholesterol. See Appendix B for a complete list of laboratory analytes.

For women of childbearing potential, a serum hCG test will be performed at screening, Week 0, and at study exit (whether at the Safety Follow-up or ET Visit). Urine hCG testing will be performed at all other visits. If a urine hCG test is positive, pregnancy will be confirmed by a serum hCG test. Follicle-stimulating hormone level will be measured at screening to confirm postmenopausal state in women ≤55 years of age.

Samples will be collected for viral serology at screening to confirm patients are negative for hepatitis B virus, HCV (patients with a confirmed history of HCV infection can be included if HCV PCR is negative for at least the last 2 years), and HIV infection.

Blood sampling procedures, including information on blood volume, collection tubes, sample processing, storage, and shipping are provided in the Laboratory Manual. Where necessary, local laboratory testing will be acceptable to monitor events of suspected drug-induced liver injury.

Technical details on laboratory parameters (methods and commercial kit[s]) will be specified in the Laboratory Manual.

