# Discontinue study drug if:

- Baseline average measurements were <2 × ULN and ALT or AST increases to >5 × baseline measurements
- Baseline average measurements were ≥2 × ULN (but <5 × ULN) and ALT or AST increases to >3 × baseline measurements
- Baseline average measurements were ≥5 × ULN and ALT or AST increases to >2 × baseline measurements
- ALT or AST increase >2 × baseline average measurements AND the increase is accompanied by a concomitant increase in TBL to >2 × baseline average measurements or the INR concomitantly increases by >0.2

AND follow the patient until resolution of signs/symptoms.

ALT = alanine aminotransferase; AST = aspartate aminotransferase; INR = international normalized ratio; TBL = total bilirubin; ULN = upper limit of normal.

Suspected drug-induced liver injury monitoring in patients with elevations in liver transaminases or bilirubin at baseline should be performed throughout the study according to the procedures summarized below.

- If patients with abnormal baseline liver indices develop elevations of AST or ALT >2 × baseline average or TBL >1.5 × baseline average values during the study, repeat testing should be performed within 48 hours.
  - o If there are persistent elevations (ALT or AST >2 × baseline average or TBL >1.5 × baseline average values) upon repeat testing, then close observation (testing and physical examination 2 to 3 times per week) should be implemented and discontinuation of study drug should be considered.
- Discontinue the study drug if any of the following occur:
  - o Baseline average measurements were  $<2 \times ULN$  and ALT or AST increases to  $>5 \times baseline$  measurements.
  - O Baseline average measurements were  $\geq 2 \times \text{ULN}$  (but  $< 5 \times \text{ULN}$  as per eligibility requirements) and ALT or AST increases to  $> 3 \times \text{baseline}$  measurements.
  - o Baseline average measurements were  $\geq 5 \times \text{ULN}$  and ALT or AST increases to  $\geq 2 \times \text{baseline}$  measurements.
  - o ALT or AST increase >2 × baseline average measurements AND the increase is accompanied by a concomitant increase in TBL to >2 × baseline average measurements or the INR concomitantly increases by >0.2.

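### The liver-enzyme models adjust only for the Visit 2 value and leave the Screening value unused, so some precision available at almost no cost is forgone on these nominal secondary endpoints

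*SAP*

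**What the plan says.** SAP 3.1.3 defines baseline for liver biopsy, imaging and biomarkers separately, then states: "For all other efficacy and safety endpoints, baseline is defined as the predose value at Visit 2 (Week 0"). Liver enzymes fall under this last rule. An earlier sample has only a fallback role: "if this value is missing, then the latest predose value is used".

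SAP 3.4.2.3 models change and percent change in AST, ALT, ALP, GGT and total bilirubin with an MMRM. Besides treatment, visit and their interaction, the adjustment terms are "biopsy fibrosis score (2 levels: F1 or F2/F3); and baseline score", that is, one baseline value. The same section opens: "Liver enzymes are assessed at Screening, Visit 2 (Week 0), Visit 3 (Week 4"), and continues through the later visits, so it lists Screening as an assessment time.

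The protocol agrees. Section 8.7 says: "Fasting hematology, biochemistry, coagulation, and lipid panels and urinalysis parameters will be evaluated at all study visits". Sections 6.2 and 6.3.1 and Appendix A schedule the biochemistry panel at Screening and Visit 2, and Appendix B shows that the panel contains all five analytes. Neither document enters the Screening enzyme value in an efficacy model.

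**The concern.** Enzyme levels vary within a patient over short periods, so one pre-dose sample is an imperfect measure of the patient's usual level. The part of that level which Visit 2 misses stays in the residual and widens the intervals for both dose comparisons. A second pre-dose value of the same analyte is already scheduled and can recover part of it.

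At stake is the width of the enzyme intervals in a dose-ranging trial. No confirmatory claim is involved: SAP 2.3.3 lists the enzymes as other secondary endpoints, and SAP 3.1.5 treats their p-values as nominal.

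**Working it through.** **The plan's own figure.** The only stated size is 88 per group (SAP 2.2.2), and it concerns the primary responder endpoint. For 18% v 40%, two-sided alpha 0.05 and 80% power, the usual two-proportion formula gives 66 evaluable per arm, and 66 / 0.75 = 88. It reproduces, and nothing below changes it. The documents give no SD, correlation or power for the enzymes.

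**Inputs (all assumed).** s = correlation of Screening with Visit 2; r = correlation of each of these with Week 52. Variances are set to 1.

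**Formulas, for the contrast at one visit.** With Visit 2 in the model, change from Visit 2 and the Week 52 value have the same residual variance.
- Visit 2 only: 1 − r²
- Visit 2 and Screening: 1 − 2r²/(1 + s)
- Proportional cut: r²(1 − s) / [(1 + s)(1 − r²)]

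The cut rises with r and falls with s, so its extremes over a rectangle of values lie at opposite corners.

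| s | r | Visit 2 only | Both | Cut |
|---|---|---|---|---|
| 0.9 | 0.5 | 0.750 | 0.737 | 1.8% |
| 0.8 | 0.6 | 0.640 | 0.600 | 6.25% |
| 0.7 | 0.6 | 0.640 | 0.576 | 9.9% |
| 0.7 | 0.7 | 0.510 | 0.424 | 17.0% |
| 0.6 | 0.7 | 0.510 | 0.3875 | 24.0% |

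At s = 0.7 and r = 0.6 the ratio is 0.576/0.640 = 0.901. That is a standard error about 5% smaller (√0.901 = 0.949), or the equivalent of 11% more patients (1/0.901 = 1.11). The 24% corner needs Screening to correlate less with Visit 2 than either does with Week 52. If r may not exceed s, the top of the range is 17.0%.

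**If Screening predicts less well than Visit 2.** Let a = corr(Visit 2, Week 52), b = corr(Screening, Week 52) and c = corr(Screening, Visit 2). Residual variance with both is 1 − (a² + b² − 2abc)/(1 − c²).
- a = 0.7, b = 0.6, c = 0.8: 1 − 0.178/0.36 = 0.506 against 0.510, a cut of 0.9%.
- b = a × c: the cut is exactly 0%.

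**Simulation check.** ANCOVA with 66 per arm, 6,000 runs per setting. With all three correlations equal to 0.5, 0.7 or 0.8, the variance ratios were 0.885, 0.835 and 0.816 (formula: 0.889, 0.830, 0.802), with no bias in either model. In the no-gain case (a = 0.7, b = 0.49, c = 0.7) the ratio was 1.007, so the extra term costs almost nothing.

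**Mean of the two as the only covariate, change still from Visit 2.** With s = 0.7 and r = 0.6:
- Variance of change: 2 − 2(0.6) = 0.80
- Covariance of change with the mean: 0.6 − (1 + 0.7)/2 = −0.25
- Variance of the mean: (1 + 0.7)/2 = 0.85
- Residual: 0.80 − 0.0625/0.85 = 0.726

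This is worse than the planned 0.640 by 13.5% (0.726/0.640 = 1.135). Visit 2 noise stays in the outcome, and the covariate no longer removes it.

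**Limit of the algebra.** It takes one visit at a time and covers absolute change. SAP 3.4.2.3 lists baseline without a visit interaction and also models percent change, so the figures are approximate for the full MMRM.

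**The case against.** The strongest reply is that a single Visit 2 covariate is standard, valid and consistent between protocol 9.2.1 and the SAP. No precision target for enzymes exists to be missed, and the p-values are nominal. All of that stands. It makes this an optional efficiency gain, not a defect.

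The gain is also unknown and may be nil. Screening can precede randomisation by up to 8 weeks (12 under Appendix G), and entry limits act on Screening values. Either may weaken its link with Week 52. This stands too, and is why the range must include 0%.

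The Screening value is not unique: several screening visits, a third stability sample, repeat testing and one rescreening are allowed. SAP 3.4.2.3 names only Visits 2, 5 and 9 as recording fasted status, so a Screening sample may be of unverified status. These points call for a tighter fix; they do not make the change costly.

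A reader might infer more from two protocol passages than they support:
- **Inclusion criterion 8.** It asks for stability "established by at least 2 samples demonstrating the following" and, when a level exceeds 1.5 × ULN, that "the variability between the 2 samples of ALT and AST does not exceed 50"%. That is an eligibility ceiling, not an estimate of noise. The two samples need not be Screening and Visit 2: they may be 2 to 16 weeks apart, and one may come from medical history. The ceiling for ALP and bilirubin is 30%, and GGT is not covered. Screening out unstable patients could even raise s and shrink the gain.
- **Appendix E.** For patients with raised baseline values, the trigger for repeat testing is that they "develop elevations of AST or ALT >2 × baseline average". This is a patient-level monitoring rule that neither defines the average nor gives a reason for it. It does not conflict with the analysis baseline, because SAP 3.1.3 uses the same Visit 2 baseline for enzyme efficacy and safety summaries.

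**Conclusion.** The point holds as a minor, optional improvement. The enzyme models use one of two scheduled pre-dose values. Adding the other cannot bias the randomised comparison, because both precede treatment.

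The likely benefit is modest. The residual-variance cut is 9.9% at the assumed central values and 1.8% to 24% over the stated range, if Screening and Visit 2 predict Week 52 equally well. It is 0% if Screening adds nothing beyond Visit 2. Every one of these figures rests on assumed correlations.

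A reader might infer that the planned enzyme analysis is biased or that the trial's conclusions are at risk. The documents support neither reading: the comparison is valid as planned, and the primary test, the six-step hierarchy and the 88 per group are untouched.

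**What to change.** Before unblinding, amend SAP 3.4.2.3 as follows:
- Keep Visit 2 as both the reference for change and a covariate.
- Add the Screening value of the same enzyme as a second covariate, defined as the last central-laboratory value before Visit 2.
- State a simple rule for a missing Screening value, and for patients whose Visit 2 baseline is already replaced by an earlier value under SAP 3.1.3.
- State whether a Visit 2 sample excluded as non-fasted counts as missing under SAP 3.1.3; the SAP leaves this open.
- Do not substitute the mean of the two values for the Visit 2 covariate while change is measured from Visit 2.

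The cost is a few lines of SAP text, one degree of freedom per model, and acceptance of a Screening sample whose fasting status may not be recorded. No new data are needed. The same step is not available for hsCRP, Pro-C3, ELF or HOMA-IR, which are first sampled at Visit 2.
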